Appendix 1: Primary outcome variable coding

Primary outcome (OCS)

Suggested wording for use in manuscripts:

The primary outcome was number of short courses of systemic corticosteroids (OCS) prescribed for asthma during the 7-month intervention period, as confirmed by hospital and/or pharmacy records (or exceptionally, reported by parents and determined to be credible by an independent clinician).

Sources of OCS events

OCS could be documented in a number of places in the study CRFs including:

REDCap database:

- Med Examination CRF (to be considered administered or prescribed prior to randomization);
- Visit and Phone Contact CRF;
- CRF OCS in Medical Records (Clinic visit 1) – should contain info about OCS dated PRIOR to Randomization, to be verified in case any typos/mistakes have been done during the data entry;
- CRF OCS in Medical Records at end of study;
- CRF Pharmacy Report (Clinic visit 1) – should contain info about OCS dated PRIOR to Randomization, to be verified in case any typos/mistakes have been done during the data entry;
- CRF Pharmacy Report at end of study;
- CRF Additional cold or asthma flareup (main redcap).

REDCap3 database (parent-reported):

- CRF Cold and Asthma Flare Up Diary For Young Children;
- CRF Summary of an asthma flare-up or cold.

Validation of OCS events

Timing:

To be considered an outcome, an OCS must be administered or prescribed after randomization but could include the day of randomization, provided it was not prescribed on the MEDEX par the study physician and there was credible information of its administration/prescription after the time of rerandomization, until (and including) the last day of the follow up window. For the purposes of OCS use, the end of the follow up window is either the date of visit 3, or if the visit 3 did not occur, the randomization date plus 7 months.

Completeness of the data:

The complete information about OCS includes the name of the medication, dose, daily frequency, duration, and route as well as reason.

Relationship with an asthma exacerbation:

(1) Inclusion

- OCS use requires a medical documentation (MedRec CRF) or by the parental report (verbally recorded in VPC or on ADYC) that the reason for its use is asthma related, defined as:
 - i. Asthma flare-up, Asthma-like diagnoses (bronchospasm, airway hyperactivity, bronchiolitis, bronchitis, wheezing, pneumonia, etc.);

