 - ii. Other diagnosis (Pneumonia, Otitis) as such indication would suggest a co-existing diagnosis of asthma
 - iii. Unknown: Handling of unconfirmed reasons of OCS use. Unless otherwise confirmed, all OCS uses will be assumed to be for asthma (i.e., pharmacy dispensing of OCS without parental report or medical record of reason for use), given the high prior probability of this reason in included participants.

(2) Excluded:

- OCS administered for treatment of conditions or other respiratory conditions (e.g. cutaneous conditions, adrenal insufficiency, anaphylaxis (anaphylactic shock), kidney disease, serum sickness, surgery, croup' or 'laryngitis' etc.) as documented in eCRF OCS documented in the medical Record (1st priority), Visit and phone contacts (less priority as self-reported) or ADYC will be excluded. Of note, if prescribed in Med examination (eCRF), then it is clearly for asthma.

Handling of Special cases

Denied administration of prescribed or dispensed OCS by parents:

If parents deny administration of identified OCS prescribed or dispensed by pharmacy, the OCS will be counted as an OCS use for the primary outcome, as per the physician intention for the child to use OCS, as this intention is the marker of moderate or severe exacerbation. (qu 10 et 11)

Delayed administration of prescribed or dispensed OCS by parents

If parents credibly report of an alternate start date than that documented in pharmacy records (for example, medication dispensed ahead of time for subsequent use as part of an action plan or prior to travel), the actual date of OCS use will be reported by parents in VPC CRF (or ADYC), and this date will be considered for primary outcome calculation. Such credible report should be documented in VPC CRF by the nurse. In this case, the concordance between the information provided verbally (VPC) or in writing (ADYC) by parents regarding the reason for, and information about, the OCS prescription will be cross-verified with the documentation of the original prescription in med records CRF (reason, name and dosage)—preferred approach—and/or Pharmacy report (OCS name, dose, duration)—secondary approach as the Pharmacy report that does not provide the reason for its prescription. If

the date of initiation has not occurred before or at Visit 3, the OCS would not be considered as OCS use during the study period. (qu 10.2.6.2)

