The list of variables related to the primary outcome calculation, including conditions to verify, is available in the [Appendix](#).

CRF specific coding rules:

- Visit and Phone Contact
phcon_steroid, phcon_steroid_2, phcon_steroid2 and phcon_steroid2_2 = 1 were used to select records where an OCS was indicated
Exclude records where reason for systemic steroids was = 2 (other condition)
ocs_start=phcon_steroid_startdat,
ocs_end=phcon_steroid_enddat,
- Med Examination
- OCS in Medical Records
ocsdoc_v1_syst_yn used to select records where an OCS was indicated
- OCS in Medical Records end of study
ocsdoc_end_syst_y used to select records where an OCS was indicated
Exclude records where reason for systemic steroids was not 1, 2 or 4, (3 was Laryngitis)
[ocsdoc_end_reason] assuming for this source that
 - if OCS is only administered, then the start date is the administration date and the duration should consider the total number of days administered as reported in qu1.1.6 (# days administered or given) including the start date
 - if only prescribed, start date is prescription date and end date calculated with the duration of prescription including prescription date.
 - if both administered and prescribed, then start date is the administration date, the total number of days considered administered is 1.1.6 (# days administered or given) and the start day of prescription is included in the duration of the prescribed medication.
 - if only prescribed, then total number of days considered date prescribed + #days prescribed - 1
- if both administered and prescribed, provide information (name, duration, etc) for each OCS
- Pharmacy Report
- Pharmacy Report end of study reporting OCS name, dose, date and number of days of prescription
- Additional cold or asthma flareup (REDCap)
- Asthma Flare-up Diary for Young Children (ADYC) (REDCap3)
- Summary of an asthma flare-up or cold (SAF) (REDCap3)

Specific variables used by CRF source

Visit and Phone Contact CRF

Variable / Field Name /	Field Attributes (Field Type, Required)
-------------------------	---

Field Label	Validation, Choices)	
10. Is the child currently taking, or have he/she taken oral, intravenous, or intramuscular STEROIDS since the last contact? [phcon_steroid_2]	1: Yes 0: No	Should be yes

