10.1 What was the reason for SYSTEMIC STEROIDS due to: [phcon_steroid_reas]	1: a. Asthma flare-up 4: b. Asthma-like diagnoses (broncho-spasm, airway hyperreactivity, bronchio-litis, or wheezing) 2: c. Other condition: (record in AHE) 3: d. Unknown	Should not be a missing value
10.1.1 Other condition: [phcon_steroid_4]	text	Should include "bronchospasm, airway hyperactivity, bronchiolitis, bronchitis, wheezing, pneumonia , otitis".
10.2 Medication (Use the generic name(s), NOT trade name(s): (To be documented when interviewing parents, but the generic name MUST be entered before submitting the form): [phcon_steroid_mednam]	1: Prednisone tablet 2: Prednisolone (Pediapred®) 3: Dexamethasone (solution or tablet) 4: Methylprednisolone (solution or tablet) 5: Solucortef 6: Other	Should not be a missing value
10.2a If other, specify: [phcon_steroid_mednam_2]	text	Should not include cefodox / magnesium sulfate / hydrocortisone, other cutaneous, nasal, ophthalmic (etc.) preparation.
10.2.1 Route: [phcon_steroid_medrout]	1: Oral 2: IV 3: IM	Should not be a missing value

10.2.2 mg per dose - - - . _ mg [phcon_steroid_meddos]	text (number)	Should not be a missing value
10.2.3 Frequency (#times/day): [phcon_steroid_medfreq]	1:1 2:2 3:3 4:4	Should not be a missing value
10.2.4 Start date: [phcon_steroid_startdat]	text (date_ymd)	Should not be a missing value
10.2.5 End date: [phcon_steroid_endat]	text (date_ymd)	Should not be a missing value
10.2.6 According to parents, the medication was administered or served by (Both answers are possible) Selon les parents, le médicament a-t-il été administré ou servi par (les deux réponses sont possibles)	[phcon_steroid_servby__1]1: Pharmacy [phcon_steroid_servby__2]1: Hospital	Should not be a missing value
10.2.6.1 Confirmation of dispensing obtained by pharmacy records: If awaiting until the end of study to obtain pharmacy records, leave this question unanswered until then [phcon_sterconfby_pharm]	1: Yes 2: No 3: Pharmacy records never obtained	Should not be a missing value
10.2.6.2 Date of dispensing based on [phcon_sterconfby_pharm_date]	1: Pharmacy records 2: Credible report by parents of an alternate start date than that documented in pharmacy records (for example, medication dispensed ahead of time for subsequent use as part of an action plan) 3: Credible report by parents of denied administration of prescribed or dispensed 4: Unconfirmed as pharmacy	Should not be a missing value

	records NEVER obtained	

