10.2.6.3 Confirmation of administration with/without dispensing obtained from hospital: If awaiting until the end of study to obtain hospital/clinic records, leave this question unanswered until then [phcon_sterconfby_hrec]	1: Yes 2: No 3: Hospital/clinic Records NEVER obtained	Should not be a missing value
10.2.6.4 Date of administration/dispensing confirmation based on [phcon_sterconfby_hosp_date]	1: Hospital/clinic records 2: Credible report by parents of an alternate start date (for example, medication dispensed ahead of time for subsequent use as part of an action plan) 3: Credible report by parents of denied administration of prescribed or dispensed medication 4: Unconfirmed as hospital / clinic records NEVER obtained	Should not be a missing value

Comment: the same coding should be applied to Q11- Q11.2.6.4.

Comment 2: in case of missing values, consider imputation if feasible (for example, the missing value for Route can be imputed based on the name of the medication).

Medical Examination CRF

Variable / Field Name / Field Label	Field Attributes (Field Type, Validation, Choices)	Required
9. Are you prescribing or recommending any systemic (oral, iv, im) corticosteroids today for the management of a CURRENT exacerbation? If Yes, specify name of the drug, dose, frequency and duration of treatment.	1: Yes 0: No	Should be Yes

[medex_rec_sys_cort]		
9. a) Systemic Corticosteroids (SCS) [medex_rec_cort_list]	1: Prednisone tablet 2: Prednisolone (Pediapred®) 3: Dexamethasone (solution or tablet) 4: Methylprednisolone (solution or tablet) 5: Other oral corticosteroids (solution or tablet)	Should not be a missing value
9.1 Name of medication [medex_rec_sys_cort_oth]	text	Should not include hydrocortisone or other unrelated medications
9. b) mg per dose, mg [medex_rec_cort_strength]	text, Required	Should not be a missing value
9. c) Frequency (#times/day) [medex_rec_cort_freq] #times/day	text	Should not be a missing value
9. d) Duration of treatment [medex_rec_cort_dur]	1: 1 day 2: 2 days 3: 3 days 4: 4 days 5: 5 days 6: >5 days	Should not be a missing value

Additional Cold or Asthma Flare-up CRF

Variable / Field Name / Field Label	Field Attributes (Field Type, Validation, Choices)	Required

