8.1.1 What was the reason for SYSTEMIC STEROIDS due to: [acafu_steroid_reas]	1a. Asthma flare-up, specify episode # below 2b. Asthma-like diagnoses (bronchospasm, airway hyperreactivity, bronchiolitis, bronchitis, wheezing, or pneumonia) 3c. Other condition: (record in AHE) 4d. Unknown	Should not be a missing value

8.1.1.1 Other condition: [acafu_steroid_oth]	text	Should include “bronchospasm, airway hyperactivity, bronchiolitis, bronchitis, wheezing, pneumonia , otitis”.
8.1.2 Medication (Use the generic name(s), NOT trade name(s): (To be documented when interviewing parents, but the generic name MUST be entered before submitting the form): [acafu_steroid_mednam]	1Prednisone tablet 2Prednisolone (Pediapred®) 3Dexamethasone (solution or tablet) 4Methylprednisolone (solution or tablet) 5Solucortef 6Other	Should not be a missing value
8.1.2.1 If other, specify: [acafu_steroid_mednam_oth]	text	Should not be a missing value
8.1.3 Route: [acafu_steroid_medrout]	1Oral 2IV 3IM	Should not be a missing value
8.1.4 mg per dose: [acafu_steroid_meddos] _____.____mg	text (number)	Should not be a missing value
8.1.5 Frequency (#times/day): [acafu_steroid_medfreq]	11 22 33 44	Should not be a missing value
8.1.6 Start date: [acafu_steroid_startdat]	text (date_ymd)	Should not be a missing value
8.1.7 End date: [acafu_steroid_endat]	text (date_ymd)	Should not be a missing value
8.1.8 According to parents, the medication was administered or served by (Both answers are possible)	acafu_steroid_servby____1: Pharmacy: 1 acafu_steroid_servby____2: Hospital: 1	Should not be a missing value
8.1.8.1 Confirmation of dispensing obtained by pharmacy records: [acafu_sterconfby_pharm]	1Yes 2No 3Pharmacy records never obtained	Should not be a missing value

8.1.8.2 Date of dispensing based on: [acafu_stecnfby_pharm_date]
	
1Pharmacy records 2Credible report by parents of an alternate start date than that documented in pharmacy records (for example, medication dispensed ahead of time for subsequent use as part of an action plan) 3Credible report by parents of denied administration of prescribed or dispensed 4Unconfirmed as pharmacy records NEVER obtained
	
Should not be a missing value

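### Appendix 1 excludes every Visit and Phone Contact record with reason code 2, although its own inclusion rules and the item 10.1.1 condition count steroid courses for bronchitis, pneumonia or otitis.

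*SAP*

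**What the plan says.** All of this is in SAP Appendix 1, to which the Primary outcome section refers for detailed coding.

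- Relationship with an asthma exacerbation, inclusion i: "Asthma flare-up, Asthma-like diagnoses (bronchospasm, airway hyperactivity, bronchiolitis, bronchitis, wheezing, pneumonia, etc".
- Inclusion ii: "Other diagnosis (Pneumonia, Otitis) as such indication would suggest a co-existing diagnosis of asthma".
- Inclusion iii, on unconfirmed reasons: "Unless otherwise confirmed, all OCS uses will be assumed to be for asthma".
- CRF specific coding rules, Visit and Phone Contact: "Exclude records where reason for systemic steroids was = 2 (other condition".
- Variable table for that form, item 10.1, code 4: "Asthma-like diagnoses (broncho-spasm, airway hyperreactivity, bronchio-litis, or wheezing". Code 2 is the other-condition option, with the diagnosis typed in item 10.1.1. Code 3 is unknown.
- Same table, item 10.1.1: the condition asks that the text include "bronchospasm, airway hyperactivity, bronchiolitis, bronchitis, wheezing, pneumonia , otitis". A comment below the table adds that "the same coding should be applied to Q11- Q11.2.6.4".
- Variable table for the Additional Cold or Asthma Flare-up form, item 8.1.1, code 2: "Asthma-like diagnoses (bronchospasm, airway hyperreactivity, bronchiolitis, bronchitis, wheezing, or pneumonia". Other condition is code 3 there.

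**The concern.** The inclusion rules and the item 10.1.1 condition both keep a code 2 record that names bronchitis, pneumonia or otitis. The form-specific line removes it without looking at the text. If that line is followed literally, the 10.1.1 condition has no effect. It also produces an odd ordering: a course whose reason nobody knows is presumed to be for asthma and kept, while one that the parent attributes to pneumonia, which the plan treats as pointing to asthma, is dropped.

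This matters because it is the derivation of the primary endpoint. Two competent programmers, one starting from the inclusion list and one from the form-specific line, could obtain different event counts from the same data.

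**Working it through.** No arithmetic applies: the SAP gives no count of code 2 records and no figure to reproduce. The check is to trace a Visit and Phone Contact record coded 2 through each rule, by the diagnosis typed in item 10.1.1.

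| Diagnosis in 10.1.1 | Inclusion rules | 10.1.1 condition | Named in code 4? | Form-specific rule | Conflict? |
|---|---|---|---|---|---|
| Bronchitis | counted (i) | qualifies | no | excluded | yes |
| Pneumonia | counted (i and ii) | qualifies | no | excluded | yes |
| Otitis | counted (ii) | qualifies | no | excluded | yes |
| Croup or laryngitis | on the exclusion list | not listed | no | excluded | no |
| Cutaneous condition | on the exclusion list | not listed | no | excluded | no |

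1. The exclusion list in Appendix 1 does not resolve the conflict. It names none of the three diagnoses, and inclusion ii expressly keeps two of them.

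2. Comparison with the other forms. The asthma-like option covers 0 of the 3 diagnoses on the Visit and Phone Contact form. It covers 2 of 3 (bronchitis and pneumonia) on the Additional Cold form and on the end-of-study medical-record form. The coding rules keep codes 1, 2 and 4 on the medical-record form, so bronchitis and pneumonia survive there. For the Additional Cold form the coding rules give no reason-code rule at all. Carrying the Visit and Phone Contact line over to it would delete its asthma-like records.

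3. From record to event. The rule drops one record from one source. The same course can still enter through the medical-record form, the pharmacy report, the Additional Cold form or the parents' diary forms. Two limits apply. Otitis has no reason code on the medical-record form. Recovery through a pharmacy report alone is uncertain, because the presumption of asthma is illustrated by dispensing for which neither parent nor record gives a reason, and here the parent gave one. Where pharmacy records were never obtained, Appendix 1 itself considers relying on the contact form.

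4. Two wording points in the same derivation, both minor.
   - The Primary outcome section separates events by seven days without saying from what point. The Appendix 1 merge rule uses two anchors, start to start (7 days) and end to start (2 days), and leaves open whether the boundary days fall inside.
   - Item 1.1.6 of the end-of-study medical-record form counts doses, but the coding rule reads it as days. This can alter a count even at few doses. Suppose 3 doses are given on one day, 5 days are prescribed, and the two durations are added (one possible reading). The true length is 1 + 5 = 6 days (days 0 to 5). Read as days it is 3 + 5 = 8 (days 0 to 7). A second course starting on day 8 is more than 7 days after the first start in both cases. The end-to-start gap is 8 − 5 = 3 days in the first case, so the events are separate, and 8 − 7 = 1 day in the second, so they merge.

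**The case against.** The strongest reply is that the SAP already has a safety net. The Primary outcome section says that self-reported courses not confirmed in medical or pharmacy records went to an independent adjudicator, as did conflicting sources. Courses known only from the Visit and Phone Contact form are such self-reports. This stands in part: the SAP does not say whether the code 2 filter runs before or after that review, so lost events are possible but not established. Double coding by two biostatisticians helps less, because two coders who both apply the written line will agree and raise no discrepancy.

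A second reply is that the coding section points to conditions to verify, and the 10.1.1 condition is one of them. Read together, the rules would exclude code 2 unless the text names a listed diagnosis. That is probably the intention, but the exclusion line does not say it.

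Third, placing the three diagnoses under code 2 is an inference from the printed options. A coordinator could have entered bronchitis or pneumonia as code 4. The 10.1.1 list also contains diagnoses that code 4 already names, which suggests that its author did not expect entries always to follow the printed options. This is fair; otitis is the firmest case.

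A reader might also infer more than the SAP supports:

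- That the different meaning of code 2 across forms is itself an error. It is not: the coding rules are set form by form, and the medical-record form is handled correctly. The gap is the missing rule for the Additional Cold form.
- That the treatment comparison is biased. Nothing in the SAP makes the filter depend on arm.
- That precision falls by a stated amount. Any such figure needs a loss share that the SAP does not give.

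**Conclusion.** The textual conflict is real and lies in the primary-endpoint derivation. As written, the Visit and Phone Contact rule drops records that the plan defines as events, for three named diagnoses. That conclusion is firm for records coded 2 that name one of them.

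The step to lost events is conditional on two things: no other source captures the course, and the filter precedes adjudication. The number affected cannot be derived. With blinding maintained, the expected effect is undercounting and poor reproducibility, not a directional bias. This should be fixed, but it does not call the analysis method into question. The two wording points on the merge window and item 1.1.6 are secondary.

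**What to change.** Before unblinding:

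1. In the CRF specific coding rules, exclude a Visit and Phone Contact record with code 2 only when the item 10.1.1 text names no diagnosis on the Appendix 1 inclusion list. Apply the same rule to the matching question 11 text.
2. State that this selection is made before records go to the adjudicator, so that qualifying self-reports reach the review.
3. State the reason-code rule for the Additional Cold or Asthma Flare-up form, noting that code 2 is asthma-like and code 3 is other condition there.
4. Minor: align the seven-day wording in the Primary outcome section with the Appendix 1 merge rule, giving the anchors and saying whether the boundary days are inside. Reconcile item 1.1.6 as days with item 1.1.6 as doses.

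The main correction costs about one line of derivation code, plus SAP wording for the other items. It uses data already collected. Making it before unblinding prevents it from looking data-driven.

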If **pharmacy records were never obtained**, we will consider accepting the OCS medications as described in the Clinic and Phone contacts eCRF, provided that the information is considered credible by the nurse and the reported reason is concordant with other document (med records or parental report) about the OCS.

Of note, given the potential subjectivity of the judgement of 'credibility', these approaches will be independently coded by two biostatisticians, to identify any rule resulting in discrepancy. Any rule resulting in discrepancies will be identified; and all OCS events in which these rules applied would be independently assessed by an independent adjudicator, whose decision will be final.

[Events with multiple 'courses'](#)

Each record of a possible OCS course will be extracted from the CRFs and added to a long file with a source, reason for administration, type of documentation, start and end date.

Once all CRF sources have been extracted, OCS courses will be evaluated to determine if they represent one event or multiple events.

Any occurrence of two or more 'courses' (whether administration, prescription, dispensing, or parent-administered), initiated with a 7-day period (between the beginning of 1st course and the beginning of the 2nd course) or within a 2-day period (between the end of a 1st course and the beginning of the 2nd course) which ever if longest, will be counted only once (and assumed to be for the same exacerbation). These approaches will be independently coded by two biostatisticians, to identify any rule resulting in discrepancy. Any rule resulting in discrepancies will be identified; and all OCS events in which these rules applied would be independently assessed by an independent adjudicator, whose decision will be final.

Following the double-coding approach, the team of [name] will prepare the list of documented OCS, in a wide format, showing all sources of OCS reporting:

- Medical Examination,
- OCS in Medical records,
- Pharmacy Report
- Visit and Phone Contact,
- Additional cold and asthma flare-up (ACAFU)
- Asthma Flare-up Diary for Young Children (ADYC) (REDCap3)
- Summary of an asthma flare-up or cold (SAF) (REDCap3)

The information from REDCap3 (ADYC and Summary CRF) will be merged with the main list of the OCS to detect special cases when information is credibly reported in REDCap3, but missing in REDCap main database.

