1.1.6 Total number of doses administered or given to parents by health care provider (for example include a dose of dexamethasone to give at home by parents) [ocsdoc_end_nb_dos] # doses	text	Should not be a missing value
1.1.7 Was the dose accompanied by a prescription (to be filled by community pharmacy), as documented in the medical chart? [ocsdoc_end_pres]	1Yes 0No	Should not be a missing value
1.1.7.1 Date of prescription[ocsdoc_end_pres_date]	text (date_ymd), Required	Should not be a missing value
1.1.7.2 Medication (Use the generic name(s), NOT trade name(s)): [ocsdoc_end_pres_med]	1Prednisone tablet 2Prednisolone (Pediapred®) 3Dexamethasone (solution or tablet) 4Methylprednisolone (solution or tablet) 5Solu cortef 6Other	Should not be a missing value
1.1.7.2 a) If other, specify[ocsdoc_end_pres_med_oth]	text	Should not include hydrocortisone or other unrelated medications
1.1.7.3 Route[ocsdoc_end_pres_route]	1Oral 2IV 3IM	Should not be a missing value
1.1.7.4 Total daily dose in mg[ocsdoc_end_pres_tot_mg]	text	Should not be a missing value

mg		
1.1.7.5 Prescription duration (# days) [ocsdoc_end_pres_dur] days	text	Should not be a missing value

Comment: the same coding should be applied to information about Medication 2 (Q1.2.1 - Q1.2.7.5) and Medication 3 (Q1.3.1 - Q1.3.7.5).

Pharmacy Report / End of Study CRF

Variable / Field Name / Field Label	Field Attributes (Field Type, Validation, Choices)	Required
Section Header: Oral Corticosteroids (OCS) Medication	1 Yes 0 No	Should be Yes
1. Has there been any serving of oral corticosteroids (OCS) medication since randomization until V3 (or 7 months after randomization if premature discontinuation) ? [pharm_ocs_end]		
1.1.1 Date of dispensing [pharm_ocs_end_dat_disp_1]	text (date_ymd), Required	Should not be a missing value
1.1.2 Medication (use the generic or trade name) [pharm_ocs_end_nam_1]	1 Prednisone tablet 2 Prednisolone (pediapred) 3 Dexamethasone (solution or tablet) 4 Methylprednisolone (solution or tablet) 5 Other (specify DIN)	Should not be a missing value
1.1.2 a) Specify [pharm_ocs_end_nam_1a]	text	Should not include hydrocortisone or other unrelated medications

1.1.4 mg per dose [pharm_ocs_end_dos_1] mg	text, Required	Should not be a missing value
1.1.5 Frequency (#times/day) [pharm_ocs_end_freq_1] #times/day	text	Should not be a missing value
1.1.6 Prescription duration (#days) [pharm_ocs_end_dur_1] days	text	Should not be a missing value

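### Appendix 1 reads a count of OCS doses as days when it sets course length, and the main text omits the 2-day part of the event-merging rule that uses that length

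*SAP*

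**What the plan says.** **Course length.** In the SAP, Appendix 1, CRF specific coding rules, the medical-records source at end of study has a rule for courses that were only administered. The course starts on the administration date and lasts the "total number of days administered as reported in qu1.1.6 (# days administered or given) including the start date". For courses both administered and prescribed, "the total number of days considered administered is 1.1.6 (# days administered or given) and the start day of prescription is included" in the length of the prescription.

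The variable table for that form, later in Appendix 1, defines the item differently: "1.1.6 Total number of doses administered or given to parents by health care provider". The variable is [ocsdoc_end_nb_dos] and its unit is doses.

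**Merging.** Appendix 1, Events with multiple 'courses', counts two courses once if they begin within 7 days of each other, start to start, or "within a 2-day period (between the end of a 1st course and the beginning of the 2nd course) which ever if longest". The Primary outcome section gives only the first part: events at least 7 days apart are separate. It does not say whether the interval runs from the start or the end of the earlier course. That section ends by referring to Appendix 1 for coding detail.

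**The concern.** The primary endpoint is the number of separate OCS-treated exacerbations per child, and the Primary outcome section ranks medical records as the preferred source. The coding rule for that source calls a dose count a number of days. Followed as written, it puts the end of an administered course too late whenever more than one dose was given per day. The 2-day part of the merging rule works from that end date, so a genuine second exacerbation can be absorbed into the first.

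The form offers no way to correct this. Its items on administered doses include a first-dose date, but no frequency and no last-dose date.

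The second issue is that the SAP states the merging rule in two versions, which classify some pairs of courses differently.

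**Working it through.** The SAP gives no figure to reproduce, so the check applies its rules directly.

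**Inputs**
- Item 1.1.6 counts doses (medical-records form, end of study).
- Appendix 1 merges on 7 days start to start or 2 days end to start, whichever is longer.
- The main text treats a gap of 7 days or more as separate.
- Doses per day: assumed 1 to 4, the options listed on two other SAP forms, Visit and Phone Contact ("10.2.3 Frequency (#times/day): [phcon_steroid_medfreq") and Additional Cold or Asthma Flare-up (8.1.5). The medical-records form does not record frequency.

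**Formulas.** Call the start of the first course day 0. A course of L days, start date included, ends on day L − 1. Take day 7 as separate, as in the main text, and the 2-day limit as inclusive. The last start day still merged is then

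max(6, (L − 1) + 2) = max(6, L + 1).

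With an exclusive 2-day limit it is max(6, L). If *n* doses are read as *n* days, *n* replaces L. A true course of 5 days or less merges through day 6.

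**Doses read as days, illustrative 5-day administered-only course**

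| Doses per day | Item 1.1.6 | Coded end day | Last start merged, as coded | Last start merged, true length | Starts wrongly merged |
|---|---|---|---|---|---|
| 1 | 5 | 4 | max(6, 6) = 6 | 6 | none |
| 2 | 10 | 9 | max(6, 11) = 11 | 6 | days 7–11 |
| 3 | 15 | 14 | max(6, 16) = 16 | 6 | days 7–16 |
| 4 | 20 | 19 | max(6, 21) = 21 | 6 | days 7–21 |

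With an exclusive 2-day limit, 10 doses wrongly merge days 7–10. The smallest dose count that matters is 6, for example two a day for 3 days: max(6, 7) = 7, so day 7 only. With 5 doses, max(6, 6) = 6 and nothing changes.

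Over courses of 1 to 5 days at 1 to 4 doses a day (20 combinations), the window is wrong in 0 + 2 + 3 + 3 + 3 = 11. It is wrong in 9 under each of the other three readings of the limits (day 7 merged or separate, 2-day limit inclusive or exclusive). These are combinations of form options, not frequencies in children.

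**Main text against Appendix 1, with correct lengths.** Read start to start, the main text merges through day 6.

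| True length | Appendix 1, inclusive 2-day limit | Starts classified differently | Appendix 1, exclusive limit | Starts classified differently |
|---|---|---|---|---|
| 5 days | 6 | none | 6 | none |
| 6 days | 7 | day 7 | 6 | none |
| 7 days | 8 | days 7–8 | 7 | day 7 |

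The Medical Examination form has an option for longer courses ("4: 4 days 5: 5 days 6: >5 days"), so the SAP foresees courses of more than 5 days.

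**The case against.** **The appendix governs.** The main text is a summary that refers to Appendix 1, the two rules agree for courses of 5 days or less, and Appendix 1 describes the outcome as short courses. This stands as a reason to rate the mismatch low. It does not remove it, because longer courses are classified differently and the summary gives no sign of a second criterion. The option for more than 5 days is weaker evidence than it looks, since baseline entries on that form are treated as preceding randomisation. The form is, however, also completed at visits 2 and 3.

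**The dosing frequencies are borrowed.** Item 1.1.6 covers doses given by the health care provider, and its own example is a dexamethasone dose to take home. Nothing in the SAP shows that provider-given courses of 10 to 20 doses are expected. An effect needs at least 6 such doses, more than one per day, and a second course inside the wrong window. This also stands: the illustrations show the mechanism, not its frequency.

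**Safeguards exist.** Two biostatisticians code independently, and an adjudicator reviews conflicting or closely spaced reports. The variable's name and unit might alert a coder. Other sources of the same course also carry end dates, and the SAP does not say which prevails. These lower the risk without removing it. Double coding exposes rules on which coders disagree, and two coders who both follow a written instruction will agree. The short interval that triggers adjudication is undefined, and the wrong merges begin only at day 7.

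**Conclusion.** Both parts hold, at minor severity. The conflict over item 1.1.6 lies within one appendix and one form, and certainty about it is high. Item 1.1.6 of the Pharmacy Report form is a duration in days, which may explain the slip, but the rule is stated for the medical-records source.

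If the rule is followed as written, the error goes one way: end dates can only be too late, so events can only be under-counted. It requires 6 or more administered doses, more than one per day, and a second course starting between day 7 and day (doses + 1). This assumes that day 7 is separate, that the 2-day limit is inclusive, and that the date derived from 1.1.6 is the one used for merging. How many children this touches cannot be computed from the SAP. The effect is probably small, and nothing suggests that it differs between arms.

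**What to change.** 1. **Primary outcome section.** State the full rule: one event if the next course starts fewer than 7 days after the start of the previous one, or within 2 days of its end, inclusive; otherwise separate.
2. **Appendix 1, Events with multiple 'courses'.** Use the same limits, so that day 7 and the 2-day boundary are unambiguous.
3. **Appendix 1, CRF specific coding rules.** Stop reading 1.1.6 as days.
   - Keep administered and prescribed courses as separate records. The existing line "if both administered and prescribed, provide information (name, duration, etc) for each OCS" points this way, though it can be read as only a listing instruction, so say it explicitly.
   - Where a prescription accompanies the dose, use the prescription's end date for the 2-day criterion, calculated as in "if only prescribed, then total number of days considered date prescribed + #days prescribed - 1". That line is written for prescription-only courses, but the rule for combined courses also includes the prescription start day in the duration, so the arithmetic is the same.
   - For administered-only courses, the dose count can matter only if the next course starts on day 7 or later and no later than day (doses + 1), given at least one dose on each day of the course. This needs 6 or more doses. Send only these cases to the existing independent adjudicator, blind to allocation. Medical records come first, with parent-reported end dates (Visit and Phone Contact 10.2.5, Additional Cold or Asthma Flare-up 8.1.7) in support.

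The cost is one sentence in the main text, matching limits in the appendix, one changed derivation step and a few more adjudicated cases. No new data are needed.
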